7. SAFETY ANALYSES

Unless otherwise specified, summaries of safety data will be provided for the Safety Analysis Set and will include data collected up to the last dose of study drug plus 30 days.

7.1. Adverse Events and Deaths

7.1.1. Adverse Event Dictionary

Clinical and laboratory adverse events (AEs) will be coded using the current version of MedDRA. System organ class (SOC), high-level group term (HLGT), high-level term (HLT), preferred term (PT), and lower-level term (LLT) will be provided in the AE dataset.

7.1.2. Adverse Event Severity

Adverse events are graded by the investigator as Grade 1, 2, 3, 4, or 5 according to toxicity criteria specified in the protocol. The severity grade of events for which the investigator did not record severity will be categorized as “missing” for tabular summaries and data listings. The missing category will be listed last in summary presentation.

7.1.3. Relationship of Adverse Events to Study Drug

Related AEs are those for which the investigator selected “Related” on the AE CRF to the question of “Related to Study Treatment.” Relatedness will always default to the investigator’s choice, not that of the medical monitor. Events for which the investigator did not record relationship to study drug will be considered related to study drug for summary purposes. However, by-subject data listings will show the relationship as missing.

7.1.4. Serious Adverse Events

Serious adverse events (SAEs) will be identified and captured as SAEs if the AEs met the definitions of SAEs that were specified in the study protocol. SAEs captured and stored in the clinical database will be reconciled with the SAE database from the Gilead Global Patient Safety (GLPS) Department before data finalization.

7.1.5. Treatment-Emergent Adverse Events

7.1.5.1. Definition of Treatment-Emergent Adverse Events

Treatment-emergent adverse events (TEAEs) are defined as follows for SEL and placebo exposures, respectively.

- SEL exposure: TEAEs are defined as 1 or both of the following:
 - Any AEs with an onset date on or after the Run-in SEL start date and no later than 30 days after permanent discontinuation of SEL
 - Any AEs leading to premature discontinuation of SEL

- Placebo exposure: TEAEs are defined as any AEs with an onset date on or after Study Day 31 (30 days after the Randomized placebo start date) and no later than 30 days after permanent discontinuation of Randomized placebo

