 Factors:

- eGFR Strata:

eGFR (mL/min/1.73 m ²)
≥ 45
≥ 30 to < 45
≥ 15 to < 30

- Albuminuria Strata: UACR < 1500 mg/g vs. ≥ 1500 mg/g
- Concomitant SGLT-2 Inhibitor Use Strata: Yes vs. No

Randomization will be stratified by the average eGFR values from Visit A and Visit B; the average values of UACR from Visit A and Visit B; and concomitant use of SGLT-2 inhibitors assessed at Visit 1. Visit A and B values for eGFR and Albuminuria will be transferred directly from the central laboratory to the interactive web response system (IWRS) for stratification but eGFR values will not be released to sites, investigators, or the sponsor.

Study Procedures/
 Frequency:

Subjects who meet eligibility criteria at Screening will enroll into the Run-in period. Starting at Visit A, subjects will receive PTM once daily for at least 7 consecutive days. Starting at Visit B, subjects will begin to receive SEL (18 mg) once daily for at least 4 weeks.

During the Run-in period, subjects will be monitored for safety and study drug compliance. After Enrollment (Visit A), subjects will be required to return to the study site on Visit B (7-14 days after Visit A), Visit C (21-28 days after Visit B), and Visit 1 (7-14 days after Visit C). Immediately prior to Visit C and Visit 1, subjects must be on SEL for at least 7 consecutive days. Visit windows are provided in the unlikely event that a subject misses a dose within 7 days prior to Visit C and Visit 1.

Following the Run-in period, eligible subjects will be randomized at the study site on Visit 1 to enter the blinded treatment phase. Subjects will have study visits on Weeks 4, 8, 12, 24, 36, 48, and every 12 weeks thereafter. SEL/PTM will continue to be administered until kidney failure (dialysis performed for at least 4 weeks, kidney transplantation, or confirmed decrease in eGFR to <15 mL/min/1.73 m² for subjects without dialysis or kidney transplantation), death, study drug discontinuation (e.g., unacceptable toxicity, subject’s refusal of treatment, kidney transplantation), or the global study end date.

Subjects who permanently discontinue study drug prior to the global study end date will have an EOT visit and a 30 Day (± 7 days) EOT Follow-up visit. They will then resume all study visits per the schedule of procedures and attend all subsequent study visits in the same manner as subjects who are still receiving study drug.

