7.3.1. Adverse Events

Following initiation of study drug and throughout the duration of the study, including the 30 Day EOS Safety Follow-up period, collect all AEs, regardless of causal relationship. AEs must be collected and reported to the eCRF database as instructed.

Regarding subjects who permanently discontinue study drug but remain on study, AEs are collected as follows:

- Full Assessments (per Section 6.7.1): Subjects continuing on study and completing full assessments, AEs are collected throughout the duration of the study including the 30 Day EOS Safety Follow-up period.
- Limited Assessments (per Section 6.7.2): Subjects continuing on study and completing limited assessments, AEs are collected throughout the duration of the study including the 30 Day EOS Safety Follow-up period.
- Remote Assessments (per Section 6.7.3): Subjects continuing on study and completing survival outcome assessments, AEs are collected through the 30 Day EOT Follow-up period.

All AEs should be followed up until resolution or until the adverse event is stable, if possible. Gilead Sciences may request that certain AEs be followed beyond the protocol defined follow-up period.

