7.1.5.2. Incomplete Dates

If the onset date of an AE is incomplete and the AE stop date is not prior to the first dosing date of Run-in SEL, then the month and year (or year alone if month is not recorded) of onset will determine whether an AE is treatment emergent.

The event is considered treatment emergent to SEL exposure if both of the following 2 criteria are met:

- The AE onset date is the same as or after the month and year (or year) of the first dosing date of Run-in SEL, and
- The AE onset date is the same as or before the month and year (or year) of the 30th day after the last dosing date of SEL

An AE with completely missing onset and stop dates, or with the onset date missing and a stop date later than the first dosing date of Run-in SEL, will be considered to be treatment emergent to SEL exposure. In addition, an AE with the onset date missing and incomplete stop date with the same or later month and year (or year alone if month is not recorded) as the first dosing date of Run-in SEL will be considered treatment emergent to SEL exposure.

The event is considered treatment emergent to placebo exposure if both of the following 2 criteria are met:

- The AE onset date is the same as or after the month and year (or year) of the 30th day after the first dosing date of Randomized placebo (Study Day 31), and
- The AE onset date is the same as or before the month and year (or year) of the 30th day after the last dosing date of Randomized placebo

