7.1.6.1. Calculation of Treatment Exposure

Treatment exposure will be calculated as follows, for SEL and placebo respectively:

- SEL: Total exposure (Patient Year) is calculated as the sum of Run-in SEL and Randomized SEL exposure time (in years) for all subjects who have been exposed to Run-in SEL and/or Randomized SEL in the Safety Analysis Set, starting from the first dosing date of Run-in SEL to the last dosing date of SEL (Run-in SEL or Randomized SEL).

In other words,

Total SEL Exposure

$$\begin{aligned}
 &= \sum_{i \in \{\text{Subjects randomized to SEL}\}} \text{Ex}(\text{first dose of Runin SEL to last dose of Randomized SEL})_i \\
 &+ \sum_{i \in \{\text{Subjects randomized to Placebo}\}} \text{Ex}(\text{first dose of Runin SEL to last dose of Runin SEL})_i \\
 &+ \sum_{i \in \{\text{Subjects not randomized}\}} \text{Ex}(\text{first dose of Runin SEL to last dose of Runin SEL})_i
 \end{aligned}$$

- Placebo: Total exposure (Patient Year) is calculated as the sum of Randomized placebo exposure time (in years) for all subjects who exposed to Randomized placebo in the Safety Analysis Set, starting from Study Day 1 to the last dosing date of Randomized placebo.

In other words,

Total Placebo Exposure

$$= \sum_{i \in \{\text{Subjects randomized to Placebo}\}} \text{Ex}(\text{first dose of Randomized Placebo to last dose of Randomized Placebo})_i$$

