7.2.2.3. Summaries of Laboratory Abnormalities

Laboratory data that are categorical will be summarized using the number and percentage of subjects in the study with the given response at Baseline and each scheduled postbaseline visit.

The following summaries (number and EAIR per 100 Patient Years) for treatment-emergent central laboratory abnormalities will be provided by lab test and exposure type (SEL or placebo); subjects will be categorized according to the most severe postbaseline abnormality grade for a given lab test:

- Treatment-emergent laboratory abnormalities
- Treatment-emergent Grade 3 or 4 laboratory abnormalities
- Treatment-emergent marked laboratory abnormalities

EAIR for treatment-emergent laboratory abnormalities will be calculated in the same manner as EAIR for TEAEs (Section 7.1.6.2).

A by-subject listing of treatment-emergent Grade 3 or 4 laboratory abnormalities will be provided by subject ID number and visit in chronological order. This listing will include all test results that were collected throughout the study for the lab test of interest, with all applicable severity grades displayed.

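### SEL adverse-event rates count events for 30 days after the last SEL dose but leave those days out of SEL person-time, so with no true difference SEL reads about 5–15% above placebo for uncommon events.

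*SAP*

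**What the plan says.** **SEL events.** SAP 7.1.5.1 counts adverse events with onset "on or after the Run-in SEL start date and no later than 30 days after permanent discontinuation of SEL". SAP 7.1.5.2 confirms the upper limit for partial dates: "the 30th day after the last dosing date of SEL".

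**SEL person-time.** SAP 7.1.6.1 sums exposure "starting from the first dosing date of Run-in SEL to the last dosing date of SEL (Run-in SEL or Randomized SEL". Its formula has three terms, for subjects randomized to SEL, randomized to placebo, and not randomized. Each term ends at that subject's last SEL dose.

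**Placebo events.** Onset must be "on or after Study Day 31 (30 days after the Randomized placebo start date) and no later than 30 days after permanent discontinuation", where the drug stopped is the randomized placebo (SAP 7.1.5.1).

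**Placebo person-time.** This is summed "starting from Study Day 1 to the last dosing date of Randomized placebo" (SAP 7.1.6.1).

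**Rate.** SAP 7.1.6.2 divides the number of subjects with at least one event by total exposure. SAP 7.1.6.3 reports the result per 100 patient-years, SEL beside placebo, for every main adverse-event category. Under SAP 7.2.2.3 the laboratory rates are "calculated in the same manner as EAIR for TEAEs", and SAP 7.2.3 also reports liver tests as exposure-adjusted rates.

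**Collection.** Protocol 7.3.1 requires sites to record adverse events in the period at issue: "Following initiation of study drug and throughout the duration of the study, including the 30 Day EOS Safety Follow-up period, collect all AEs".

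**The concern.** A rate is interpretable only if the time in which an event can be counted is also the time in the denominator. For SEL it is not: up to 30 days per subject appear in the event window only. A 30-day tail of this kind would partly cancel if both groups carried it. Here it does not, because the placebo window starts 30 days late and ends 30 days late, which leaves its length equal to the placebo denominator.

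Placebo-randomized subjects show the inconsistency most clearly. Events in their first 30 days on placebo go into the SEL numerator, while the same 30 days go into the placebo denominator.

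These rates are the plan's main SEL-placebo safety comparison. In the earlier Phase 2 study in diabetic kidney disease, SAEs were already more frequent on pooled SEL than on placebo (25.8% vs 18.8%, Protocol Table 1-3). An artefact in the same direction makes any difference seen here harder to read.

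**Working it through.** **The plan's own figures.** The documents give no value for these rates or for their bias. The one design figure used here is the sample size. Recomputing the stated power (difference 3.7, SD 10, one-sided 0.15) gives 98.5% at 150 per arm and 97.2% at 127 per arm, in line with the stated 99% and 97% (SAP 1.3).

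**Inputs**
- 150 subjects per arm (SAP 1.3).
- Run-in SEL of 28–42 days. SEL starts at Visit B, followed by "Visit C (21-28 days after Visit B), and Visit 1 (7-14 days after Visit C" (Protocol Synopsis), so 21 + 7 = 28 and 28 + 14 = 42. The midpoint, 35 days, is used.
- Mean randomized treatment d is not stated. The planned minimum is 48 weeks (Protocol 3.3), the primary endpoint runs through Week 84 (SAP 6.1.1), and visit windows run to Week 168 (SAP Table 3-2).
- Assumed: the same constant hazard on both treatments, full 30-day follow-up after the last dose, and no run-in failures in the base case.

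**Formula for uncommon events.** Expected subjects with an event are proportional to window length, so each rate is biased by the factor window/denominator.
- SEL window = 150 × (35 + d + 30) + 150 × (35 + 30)
- SEL denominator = 150 × (35 + d) + 150 × 35
- Gap = 300 × 30 = 9,000 days, whatever d is
- Placebo window = placebo denominator = 150 × d, factor 1.000
- SEL/placebo ratio = 1 + 60/(70 + d)

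| Mean randomized treatment | SEL window (days) | SEL denominator (days) | Ratio |
|---|---|---|---|
| 48 weeks (d = 336) | 69,900 | 60,900 | 1.148 |
| 84 weeks (d = 588) | 107,700 | 98,700 | 1.091 |
| 96 weeks (d = 672) | 120,300 | 111,300 | 1.081 |
| 168 weeks (d = 1,176) | 195,900 | 186,900 | 1.048 |

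**Sensitivity at 48 weeks**
- Run-in SEL of 28 days: 1 + 60/(56 + 336) = 1.153. Of 42 days: 1 + 60/(84 + 336) = 1.143.
- Early stopping: if 28.9% stop halfway, mean d = 336 × (1 − 0.289/2) = 287 and the ratio is 1 + 60/(70 + 287) = 1.168. The 28.9% is the SEL 18 mg discontinuation rate in the earlier study (Protocol 1.2.3.2.2); stopping at the halfway point is assumed.
- Run-in failures: an assumed 50 subjects with 20 SEL days each give (69,900 + 50 × 50)/(60,900 + 50 × 20) = 72,400/61,900 = 1.170.

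**More frequent events.** With hazard λ, each subject contributes 1 − exp(−λt) to the numerator, where t is that subject's window. At 0.3/year the ratio as planned is 1.141 at 48 weeks and 1.090 at 84 weeks, so the bias is not confined to rare events.

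**After matching person-time to the event windows**
- Uncommon events: 1.00.
- Hazards up to 0.3/year: 0.99–1.01.
- A very common category, assumed 1.6/year: 1.006 (48 weeks) and 1.055 (84 weeks) with no run-in failures; 1.031 and 1.088 with 50. This residual arises because subjects keep accruing time after their first event. Stopping time at the first event gives 1.000.

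**The case against.** The strongest case against acting is that little turns on it. The SAP plans no ratio, interval or test for these rates. Subject counts are shown beside them, by-subject listings are planned, and the adverse events of special interest in SAP 7.1.7 are reported as counts and percentages. The uncounted time is 9,000/365.25 = 24.6 patient-years. At 1 event per 100 patient-years that is about 0.25 of one extra SEL subject; at 5 per 100 it is about 1.2, against roughly 13.5 expected in the 270 patient-years (98,700 days) of the 84-week scenario. For one uncommon event, chance variation is much larger. The error also makes SEL look worse, so it cannot hide a SEL harm.

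All of that stands, and it limits the point to interpretation. It does not make the rate correct: the shift is systematic, runs the same way in every category, and applies equally to the more frequent categories, where it is a larger number of subjects.

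Three further cautions also stand.
- Subjects who die, withdraw or are lost do not supply a full 30-day tail, so the base-case ratios assume complete follow-up.
- The 5–15% range rests on assumed mean exposure and is not a ceiling.
- Two other SEL-only rules remain after the fix: events leading to SEL discontinuation count without a date limit (SAP 7.1.5.1), and events with both dates missing default to SEL (SAP 7.1.5.2).

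**Conclusion.** The concern holds. As written, SAP 7.1.5.1 and 7.1.6.1 use different time windows for the SEL numerator and denominator, the placebo pair matches in length, and nothing elsewhere in the SAP corrects the difference. The direction is certain: the SEL rate is inflated relative to placebo.

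The size is a scenario range of about 5–15% for uncommon events, for mean randomized treatment from 168 weeks down to 48 weeks. It rests on equal constant hazards, 150 per arm, 35 days of run-in SEL, no run-in failures and full 30-day follow-up; early stopping or run-in failures take it to about 17% at 48 weeks. The range should not be applied to the laboratory and liver rates. Their windows and denominators have the same mismatch, but those abnormalities are detected only at visits.

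This should be fixed. It affects how the safety tables are read, not a formal test.

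**What to change.** In SAP 7.1.6.1, define person-time over the same windows as the events:
- **SEL:** from the first run-in SEL dose to the earlier of last SEL dose + 30 days and last contact, for all three groups in the formula.
- **Placebo:** from Study Day 31 to the earlier of last placebo dose + 30 days and last contact.

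SAP 4.2.1 already defines a last contact date that can be used. Apply the same denominators in SAP 7.2.2.3 and 7.2.3, whose event windows have the same form. For very common categories such as any treatment-emergent event, also stop each subject's time at the first event; otherwise a ratio of up to about 1.09 can remain at 48–84 weeks, and more with longer treatment.

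The cost is SAP wording and reprogramming of the two exposure-time variables, plus a separate denominator for each very common category. No new data are needed. SEL rates for uncommon events would fall by about 5–13% (1 − 1/1.048 to 1 − 1/1.148).

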8.6.2. Adverse Events

Clinical and laboratory adverse events will be coded using the Medical Dictionary for Regulatory Activities (MedDRA). System Organ Class (SOC), High-Level Group Term (HLGT), High-Level Term (HLT), Preferred Term (PT), and Lower-Level Term (LLT) will be attached to the clinical database.

Events will be summarized on the basis of the date of onset for the event. Treatment-emergent adverse events (TEAEs) are defined as one or both of the following:

- Any AEs with an onset date on or after the study drug start date and no later than 30 days after permanent discontinuation of study drug
- Any AEs leading to premature discontinuation of study drug. Summaries (number and percentage of subjects) of TEAEs (by SOC, and PT) will be provided by treatment group. TEAEs will also be summarized by relationship to study drug and severity. In addition, TEAEs leading to premature discontinuation of study drug will be summarized and listed.

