3.8. Analysis Visit Windows

3.8.1. Definition of Study Day

Study Day will be calculated from the first dosing date of blinded SEL/placebo treatment and derived as follows:

- For postdose study days: Assessment Date – First Blinded SEL/placebo Dosing Date + 1
- For days prior to the first dose: Assessment Date – First Blinded SEL/placebo Dosing Date

Therefore, Study Day 1 is the day of first dose of blinded SEL/placebo administration.

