7.1.6.3. Summaries of Exposure-Adjusted AE Incidence Rate

A brief, high-level summary of the number of subjects who experienced at least 1 TEAE in the categories described below will be provided by exposure type (SEL or placebo) and overall. EAIRs (per 100 Patient Years) will also be presented. All deaths observed in the study, as well as EAIRs per 100 Patient Years will also be included in this summary by exposure type (SEL or placebo) and overall.

The number subjects who experienced at least 1 TEAE in the AE categories described below will be provided and summarized by SOC, PT, by exposure type (SEL or placebo) and overall. EAIRs (per 100 Patient Years) for AEs in these categories will also be provided.

- TEAEs
- TEAEs with Grade 3 or higher
- TE treatment-related AEs
- TE treatment-related AEs with Grade 3 or higher
- TE SAEs
- TE treatment-related SAEs
- TEAEs leading to premature discontinuation of study drug
- TEAEs leading to temporary interruption of study drug
- TEAEs leading to Death

Multiple events will be counted only once per subject per exposure type in each summary. Adverse events will be summarized and listed first in alphabetic order of SOC, and then by PT in descending order of total frequency within each SOC. For summaries by severity grade, the most severe grade will be used for those AEs that occurred more than once in an individual subject during one exposure type (SEL or placebo) during the study.

In addition to the above summary tables, all TEAEs, TE SAEs, TE treatment-related AEs, and TE treatment-related SAEs will be summarized by PT only, in descending order of total frequency.

In addition, data listings will be provided for the following in the All Enrolled Analysis Set:

- All AEs, indicating whether the event is treatment emergent
- All AEs of Grade 3 or above

- All SAEs
- All Deaths
- All AEs leading to premature discontinuation of study drug
- All AEs leading to temporary interruption of study drug

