7.7. Changes From Protocol-Specified Safety Analyses

There are no deviations from the protocol-specified safety analyses.

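### The SAP drops the protocol's leads-to-discontinuation clause for placebo but declares no deviation, so a few placebo stops are tabulated only under SEL or in neither column (minor)

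*SAP*

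**What the plan says.** Protocol 8.6.2 gives two routes to a treatment-emergent AE: onset within the dosing period plus 30 days, or "Any AEs leading to premature discontinuation of study drug". The second route does not depend on the drug.

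SAP 7.1.5.1 splits the definition by exposure. SEL keeps both routes: "Any AEs with an onset date on or after the Run-in SEL start date and no later than 30 days after permanent discontinuation of SEL", or "Any AEs leading to premature discontinuation of SEL". Placebo has the onset route only: "TEAEs are defined as any AEs with an onset date on or after Study Day 31 (30 days after the Randomized placebo start date"), with the window closing 30 days after the last randomized placebo.

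SAP 7.1.6.3 then tabulates "TEAEs leading to premature discontinuation of study drug", and a matching row for temporary interruptions, by exposure type (SEL or placebo) and overall. SAP 7.7 states: "There are no deviations from the protocol-specified safety analyses".

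**The concern.** Every subject randomized to placebo has just come off run-in SEL, so the SEL onset window is still open for about the first 30 days on placebo. An AE that starts in that period and leads the subject to stop placebo is a SEL event under the SAP and not a placebo event. The reader of the discontinuation table sees it under a drug that the subject was no longer taking. An AE that began before run-in SEL and later leads to stopping placebo meets neither definition and drops out of the table. Under the protocol's rule both would be treatment-emergent because study drug was stopped.

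Safety and tolerability is a secondary objective, and stops for AEs are an ordinary measure of it. The report could carry two counts of AE-related stops that disagree, one by exposure type and one by treatment group, under a statement that nothing was changed from the protocol.

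**Working it through.** **Dates.** SAP 3.8.1 sets Study Day = date minus first blinded dosing date, plus 1: "Therefore, Study Day 1 is the day of first dose of blinded SEL/placebo administration". Placebo start + 30 days is therefore Study Day 30 + 1 = 31, which reproduces the SAP's figure. If the last run-in SEL dose is on Day -1, the SEL window (last dose + 30 days) closes on Day 30, with no gap or overlap. If it is on Day 1, the window closes on Day 31, and a Day 31 onset meets both definitions.

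**Classification.** Take a placebo subject with run-in SEL from Day -35 to Day -1 who stops placebo on Day 60 because of an AE:

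| AE onset (Study Day) | SEL TEAE | Placebo TEAE |
|---|---|---|
| -40 (before run-in SEL) | no | no |
| -20, 1, 15, 30 | yes | no |
| 31, 45 | no | yes |

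No passage in the SAP reassigns any of these events. Two mechanisms are at work. The SEL onset window puts the second row under SEL. The missing placebo clause keeps the first two rows out of the placebo column.

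**Size.** The documents do not give the timing of AE-related stops, so this is an illustration.

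Inputs: in the earlier DKD study's placebo group, 9.4% had AEs leading to discontinuation (protocol 1.2.3.2.4) and 22.4% stopped drug for any reason (1.2.3.2.2), in a study with 48 weeks of treatment; 150 subjects per arm (SAP 1.3). Assumptions: constant hazards, no drug effect, and the stop date taken as the AE onset date.

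- 48 weeks = 336/365.25 = 0.920 years.
- AE-stop hazard: -ln(1 - 0.094)/0.920 = 0.107 per year.
- All-cause stopping hazard: -ln(1 - 0.224)/0.920 = 0.276 per year.
- Mean time on drug to Week 48: 0.224/0.276 = 0.81 years, or 121.9 patient-years for 150 subjects.
- Placebo AE stops by Week 48: 0.1073 × 121.9 = 13.1.
- With onset on Days 1-30: 150 × 0.1073 × 30/365.25 = 1.3.
- Share: 1.3/13.1 = 10%.

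Ignoring other reasons for stopping, the total is 150 × 8/85 = 14.1 and the share is 9%. If AE stops cluster early, at an assumed 20% to 30% with onset before Day 31, then 0.2 × 13.1 = 2.6 to 0.3 × 13.1 = 3.9 subjects would move. AEs that start during run-in SEL and later stop placebo would add to these figures; the documents give no basis for a number.

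**The case against.** The 30-day carry-over is not arbitrary. It mirrors the protocol's own post-treatment window, and crediting events soon after SEL to SEL is cautious for the investigational drug. Assigning every event to the drug being taken has the opposite fault: an AE that begins on run-in SEL and leads to stopping on Day 2 would be shown as a placebo stop, hiding possible SEL intolerability. This stands, and it is why the carry-over rule should stay in the general TEAE tables.

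True stops are also visible elsewhere. SAP 4.1 gives reasons for stopping drug by randomization status and treatment group, with a by-subject listing. SAP 7.1.6.3 lists all AEs leading to discontinuation and to interruption. This stands too and limits the harm. The randomization criteria in protocol 4.4 (no permanent stop in the run-in, no ongoing clinically significant illness judged to matter) narrow the run-in-onset route without closing it.

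A reader might infer a rate bias against SEL. With five weeks of run-in SEL for 300 subjects (300 × 35/365.25 = 28.7 patient-years), the same model gives SEL (13.08 + 3.08 + 1.31)/150.6 = 11.6 and placebo (13.08 - 1.31)/121.9 = 9.7 per 100 patient-years, although the true rates are equal. That gap does not belong to this point. Move the 12.2 placebo patient-years of Days 1-30 to the column that takes those events, and the rates become 17.47/162.8 = 10.7 and 11.77/109.7 = 10.7. The gap comes from SAP 7.1.6.1 starting placebo time on Day 1, which is a separate matter.

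**Conclusion.** The point holds as a minor one. The SAP omits a protocol clause for one of the two drugs, and the statement in SAP 7.7 is wrong on this. The consequence is misplacement of about 1.3 of 13 placebo AE stops by Week 48, resting on the constant hazard, the earlier study's rates and 150 per arm. The events affected are those with onset from the start of run-in SEL to Day 30 (SEL column only) and those with onset before run-in SEL (neither column).

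Two stronger readings are not supported. First, the missing clause does not itself send events to the SEL column; the SEL onset window does, and adding the clause alone would make such an event treatment-emergent for both exposures. Second, the interruption row is not a departure from the protocol's discontinuation clause. It has the same onset-based attribution, but neither document has an interruption clause for any drug.

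**What to change.** 1. In SAP 7.1.5.1, add to the placebo definition a clause covering AEs that lead to premature discontinuation of randomized placebo, matching the SEL clause.
2. In SAP 7.1.6.3, add a summary of AEs leading to discontinuation or interruption during the Randomization Phase, by randomized arm (the drug being taken when it was stopped or held). Keep the 30-day carry-over attribution in the general TEAE tables, and flag any AE that meets both definitions.
3. Declare the change in SAP 7.7. If the SAP is already final, record it in the CSR, as SAP section 1 provides.

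The cost is one extra table and some programming. The AE-to-action link and the date of each action must be available; the AE form is not in the documents, so this should be checked. The same AE can then appear under SEL in the TEAE table and under placebo in the stop table, which needs a footnote.
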